2.3 Sample Size Determination

The sample size was selected in a manner that will maximize information for selected starting doses while minimizing exposure of children to ineffective starting doses. The initial number of subjects per age/dose cohort will be 3. When the DSMC agrees that a safe and effective starting dose (i.e., the recommended dose) has been identified for a particular age group, nine additional subjects in the age group will receive the selected starting dose. This will yield a total of 12 subjects per age group. The total sample size for all three age groups could be as low as 36, if the first dose is chosen as safe and effective, and up to 54 if all three dose levels are studied for each age group.

With a sample size of 12 subjects in each age cohort at the identified efficacious and safe starting dose, and assuming a 100% probability of achieving potassium level within the normal range (3.8 – 5.0 mEq/L), the lower bound of the 95% exact confidence interval for achieving this success rate is 73%.

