--

	stopping patiromer treatment (Follow-up Visit 2). All subjects who withdraw early from treatment will enter the Follow-up Period.
DSMC Review / Starting Dose Level Assessment:	
The DSMC will determine a recommended starting dose for each age group. After three subjects at a given starting dose level provide data from the 14-Day PD / Dose Finding Phase, the DSMC will evaluate safety and PD data, including achievement of serum potassium within the target range (serum K⁺ 3.8 – 5.0 mEq/L) and the PD response pattern as well as the number of subjects requiring dose titration. Based on this review, the DSMC will provide a recommendation to evaluate another starting dose in the age group or to evaluate the current starting dose in additional subjects in the age group. Details regarding DSMC review criteria will be described in a charter and are summarized in the DSMC section of the protocol (Section 8.6).
 
The initial number of subjects for each starting dose level will be three, and up to three starting doses per age group can be evaluated. Subject screening will pause periodically throughout the study to allow for preparation of data and DSMC review and provision of recommendations. Any subjects who are in the Screening Period when the pause is announced may be enrolled provided they meet all eligibility criteria. When the Study Management Committee (SMC; see Section 8.5) and DSMC agree upon the recommended patiromer starting dose for a particular age group based upon safety and PD data review, nine additional subjects (or fewer if more than three subjects were initially enrolled) will be added in that age group to receive the recommended patiromer starting dose. Subjects will not be enrolled into higher starting dose levels once the recommended patiromer starting dose is determined for a particular age group. This will yield a total of 12 subjects per age group at the recommended starting dose and a maximum of 18 subjects per age group.
 
Based on findings from the 12 – < 18 years of age cohort, the DSMC will provide a recommendation to initiate dosing in a younger age group, and provide further guidance regarding the starting doses and titration increments for the younger age groups.
 
In addition, the DSMC will review safety and PD data on an ongoing basis during the Long-Term Treatment Phase for all age groups.

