8.6.1 Dose Escalation

Evaluation of Starting Dose Levels:

During the 14-day PD / Dose Finding Phase the Investigator will be allowed to up-titrate the patiromer dose according to a protocol-specified algorithm. A description of the patiromer dose titration algorithm is provided in Section 5.2.1.

After three subjects complete their 14-Day PD / Dose Finding Phase, PD, dosing and safety data will be provided to the DSMC. The DSMC will evaluate these data, as well as the number of subjects requiring dose titration. Based on its review, the DSMC will determine if the starting dose for subjects under review was acceptable for a recommended starting dose, in which case nine additional subjects (or fewer if more than three subjects were initially enrolled) in the same age group will be enrolled at the same starting dose. If the DSMC determines that the starting dose and/or titration pattern did not result in an acceptable PD response, but the safety was acceptable, the DSMC will provide a recommendation to evaluate the next higher starting dose in the age group.

Subject screening will pause periodically throughout the study to allow for preparation of data and DSMC review and provision of recommendations. Any subjects who are in the Screening Period when the pause is announced may be enrolled provided they meet all eligibility criteria. Details regarding DSMC review criteria are described in the DSMC charter.

The DSMC will evaluate the following subject-level parameters in assessing a patiromer starting dose level:

- Achieving a target serum potassium range of 3.8 – 5.0 mEq/L
- Clinically relevant decrease in serum potassium
- Number of dose up-titrations above the starting dose
- Patient safety information

The DSMC will consider the baseline and change in serum potassium level in determining if an observed decrease in serum potassium is clinically relevant for subjects that do not achieve the target potassium range. In addition, the DSMC will consider the proportion of subjects that had up-titrations of patiromer to ensure a recommended starting dose is close to the effective dose (e.g., up-titrations required in all three subjects may suggest the starting dose was too low).

Section 5.2 describes the planned starting doses in all age groups. The DSMC will recommend the starting doses for the 6 – <12 year old age group upon evaluation of PD and safety data for the

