7 STATISTICAL METHODOLOGY AND STATISTICAL ANALYSES

7.1 General Considerations and Statistical Methods

For continuous variables, descriptive statistics will include the number of subjects, mean, standard deviation (SD), standard error (SE), median, 25th, 75th percentiles, minimum and maximum.

For categorical variables, descriptive statistics will include frequencies and percentages in each category.

When mean change from baseline is assessed, a subject will be included in the analysis if he/she has a baseline and a post-baseline measurement.

All statistical tests will be conducted at a two-sided alpha level of 0.05 and 95% confidence intervals will be utilized, unless otherwise stated.

All table results, unless otherwise specified, will be displayed by age cohort, starting dose, and overall. For subjects who transition to maintenance hemodialysis or peritoneal dialysis during the study, their data after the start of dialysis will be excluded from summary tables and will be included in listings only.

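### At the recommended starting dose, the children whose Day 14 potassium led to the dose being accepted are pooled with those enrolled afterwards, so the Day 14 estimates lean favourable by an amount the documents do not fix

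*SAP*

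**What the plan says.** SAP 2.3 sets the cohort sizes: "The initial number of subjects per age/dose cohort will be 3", and after a dose is agreed "nine additional subjects in the age group will receive the selected starting dose. This will yield a total of 12 subjects per age group". The DSMC review part of the protocol synopsis says the same: "This will yield a total of 12 subjects per age group at the recommended starting dose and a maximum of 18 subjects per age group". That part and Protocol 3.2.2 add that the expansion may be smaller than nine if more than three children were enrolled at first.

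Protocol 8.6.1 describes the decision: "The DSMC will evaluate the following subject-level parameters in assessing a patiromer starting dose level". Four parameters follow: potassium in the 3.8 – 5.0 mEq/L target range, a clinically relevant potassium decrease, the number of up-titrations, and safety. If the response is unacceptable but safety is acceptable, the next higher dose is tried. Detailed criteria are left to the DSMC charter.

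The efficacy population is every dosed child (SAP 4.1). On display, SAP 7.1 says: "All table results, unless otherwise specified, will be displayed by age cohort, starting dose, and overall". SAP 7.9.1 summarises the Day 14 change with a mean, SD and 95% confidence interval. SAP 7.9.2 gives in-range proportions with Clopper-Pearson intervals. Neither separates children treated before the dose decision from those treated after it, and neither comments on the selection.

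**The concern.** The first two DSMC parameters are the endpoint variables themselves. The target range defines the Day 14 secondary endpoint, and the potassium decrease is the primary one. A dose gains nine more children because its first three did well enough, and those three are then counted in the result for that dose. Their contribution is conditional on a favourable outcome; the later children's is not.

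The two endpoints move in opposite numerical directions. The in-range proportion is pushed up. The mean change, expected to be negative, is pushed down, toward a larger reduction.

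The result at the recommended dose is what the expansion cohort exists to estimate, and Protocol 1.2 says that no earlier patiromer study has been done in children. A reader of the final table would see 12 children and an exact interval, with no sign that some of them determined the choice of dose.

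**Working it through.** **The plan's own figures.** For 12 of 12 in range, the two-sided 95% exact lower bound is 0.025^(1/12) = 73.5%, which agrees with the stated 73%. The totals also reproduce: 3 × (3 + 9) = 36 and 3 × (3 + 3 + 12) = 54.

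**Direction.** Let X be the number in range among the first three, p the true in-range rate, and a(X) the probability of acceptance given X. Then

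E[X | accepted] = 3p + Cov(X, a(X)) / P(accepted).

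If a(X) rises with X and 0 < p < 1, the covariance is positive. The bias of the pooled proportion is (E[X | accepted] − 3p)/12. The nine later children have expectation p whatever the rule.

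**Size for the proportion.** The documents give no numeric rule, so two are assumed: at least 2 of 3 in range, and 3 of 3. The true rates are also assumed. One of them, 76%, is the adult Week 4 in-range figure in Protocol 1.2, used only as an illustration.

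- 2 of 3, p = 50%: E[X | accepted] = (2 × 0.375 + 3 × 0.125)/0.5 = 2.25, so the bias is (2.25 − 1.5)/12 = 6.25 points.
- 2 of 3, p = 76%: E[X | accepted] = (2 × 0.4159 + 3 × 0.4390)/0.8548 = 2.514, so the bias is (2.514 − 2.28)/12 = 1.9 points.
- 3 of 3: the bias is 3(1 − p)/12, which is 12.5 points at 50% and 6.0 at 76%.

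| True rate | Bias, 2 of 3 (points) | Bias, 3 of 3 (points) |
|---|---|---|
| 50% | 6.25 | 12.5 |
| 60% | 4.4 | 10.0 |
| 70% | 2.8 | 7.5 |
| 76% | 1.9 | 6.0 |
| 80% | 1.4 | 5.0 |
| 90% | 0.4 | 2.5 |
| 100% | 0 | 0 |

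A laxer rule, at least 1 of 3, gives 1.8 points at 50% and 0.3 at 76%.

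**Interval coverage, by enumeration.** Under 2 of 3, coverage is at least 96% at every tabulated rate from 50% to 90%. Under 3 of 3 it is 91% at 50%, 93% at 60%, and at least 95.9% at the tabulated rates from 70% to 90%. The 91% can be checked by hand. The lower limit exceeds 50% when 10 or more of 12 are in range. With the first three in range, that needs 7 or more of nine: (36 + 9 + 1)/512 = 9.0%. Exact coverage moves in steps, so there is one further short dip between the tabulated rates: just below 73.5%, a 12 of 12 result excludes the truth, and 0.73^9 = 5.9%, giving about 94%.

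**Mean change.** The pooled bias is (3/12) × E[mean of three − true mean | accepted]. Assume SD 0.5 mEq/L and acceptance when the mean reduction of the three exceeds the true mean. Then the bias in the three is (0.5/√3) × 0.798 = 0.230, and in the 12 it is 0.058 mEq/L. The standard error of the 12-child mean is 0.5/√12 = 0.144. Varying the SD from 0.4 to 0.6 and the threshold within one standard error gives about 0.02 to 0.13 mEq/L. If acceptance depends only on the Day 14 range (baseline 5.5, SD 0.35 assumed), simulation gives 0.03 to 0.09 mEq/L for a true change of −0.5 and at most 0.013 for −1.0.

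**Price of leaving the first three out.** The exact lower bound for 9 of 9 is 0.025^(1/9) = 66.4%, against 73.5% for 12 of 12. With SD 0.5, the t half-width is 2.306 × 0.5/√9 = 0.38 mEq/L, against 2.201 × 0.5/√12 = 0.32.

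**The case against.** **The rule is unseen, and the DSMC uses judgement.** Safety and up-titrations count as well as response, and dose titration before Day 14 means that an in-range child need not count in favour of the starting dose. This stands as to size, and every figure above is illustrative. It does not change the sign, provided that better response makes acceptance more likely. A dose expanded whatever its first results showed, which might happen at the highest level, would carry no such bias.

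**The pooled estimate is usually the more accurate one.** This stands. Root mean squared error, pooled 12 against the nine later children:

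- 2 of 3: 0.116 against 0.142 at 76%, and 0.144 against 0.167 at 50%.
- 3 of 3 at 76%: √(0.06² + 9 × 0.1824/144) = 0.122 against 0.142.
- 3 of 3 at 50%: 0.177 against 0.167, the only one of these cases in which the nine do better.

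A reader might infer that the nine should replace the 12 as the main result. These figures do not support that.

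**The 73% figure.** A reader might also infer that the precision statement in SAP 2.3 is wrong because only nine children are unselected. It is explicitly conditional on a 100% success probability. At that rate every first group passes and the bias is exactly zero.

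**Nothing is hidden, and nothing is tested.** The tables are by age cohort as well as starting dose, doses that fail review stay in them, and potassium values are listed. The efficacy endpoints are summarised descriptively, so there is no type I error to inflate. What remains is a matter of estimation and labelling.

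**The later children are not a clean group of nine.** Children in screening when a pause is announced may still be enrolled, and the SMC may extend a cohort (Protocol 3.2.2 and 8.5). This stands, and it shapes the definition in the fix.

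**Conclusion.** The point holds in a limited form. At the recommended starting dose, the children whose Day 14 data led to acceptance are pooled with those enrolled later, without a separate view or a caveat. If the decision favours response and the true in-range rate is below 100%, the pooled proportion is too high and the pooled mean reduction too large, in expectation.

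The documents do not fix the size. Under the assumed 2-of-3 rule the effect on the proportion is modest at the rates tabulated and the interval keeps its nominal coverage. Under the assumed 3-of-3 rule the bias reaches 12.5 points at a true rate of 50%, and among the tabulated rates coverage is below 95% only at 50% and 60%. The mean-change bias is smaller than the standard error of the 12-child mean in the cases examined. A reader might infer a large, known overstatement of the trial's main result; the documents do not support that. They support a small supplementary display and a sentence of disclosure.

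**What to change.** Keep the 12-child summary as the main result. In SAP 7.9.1 and 7.9.2 add, for the Day 14 primary and secondary endpoints at the recommended starting dose in each age cohort, a supportive summary restricted to children whose Day 14 data were not in the DSMC review that selected the dose. Define the group by that criterion and not by enrolment order. It will hold about nine children, possibly fewer. Add one sentence stating that the 12-child result includes the children used for dose selection and that its interval does not account for the selection. Visits after Day 14 can be left as planned.

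The cost is one flag in the analysis dataset and one extra column. It needs no new data and no change to conduct, and can be added before database lock. The drawback is the wider interval in the smaller group, which is why it should stand beside the pooled result and not replace it.

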3 INTERIM ANALYSES, FINAL ANALYSIS AND UNBLINDING

This is an open-label multiple dose study to evaluate the pharmacodynamic (PD) effects, safety, and tolerability of patiromer. Subjects and sites study staff will not be blinded to treatment assignment. The data will be periodically evaluated by an independent external data safety monitoring committee (DSMC) and by an internal Relypsa safety committee (SMC). The schedule of the data reviews is detailed in the protocol and in the DSMC charter.

No efficacy interim analysis is planned for this study. The final analysis will be performed after database lock.

4 ANALYSIS SETS

4.1 Efficacy Population

The efficacy population will include all subjects who have taken at least one dose of patiromer.

4.2 Safety Population

The safety population will include all subjects who have taken at least one dose of patiromer.

The safety population and efficacy population are same in this study, so all analyses will be displayed with one population, i.e. safety population.

4.3 Protocol Deviations

All protocol deviations will be recorded in the protocol deviation log. Prior to database lock, all protocol deviations will be compiled.

The following deviations are considered, a priori, to be important protocol deviations:

- Violations of initial informed consent
- Enrolled in violation of the entry criteria
- Administration of a prohibited medication to a study subject potentially affecting the primary and secondary efficacy endpoints
- Study subjects not discontinuing study medication when they met protocol criteria for stopping study treatment
- Dosing with study drug after a study subject's withdrawal from the study

5 ENDPOINTS AND VISIT WINDOWS

5.1 Efficacy Endpoints

5.1.1 *Primary Efficacy Endpoint*

Changes from baseline to Day 14 in serum potassium levels will be summarized by starting dose and age group using descriptive statistics. Baseline potassium will be the last non-missing central laboratory serum potassium value prior to first dose of patiromer. Descriptive statistics include mean, standard deviation, and 95% confidence intervals.

5.1.2 *Secondary Efficacy Endpoints*

- Proportion of subjects with serum K⁺ levels in the range of 3.8 – 5.0 mEq/L at Day 14 (Initial PD / Dose Finding Phase)
- Proportion of subjects with serum K⁺ levels in the range of 3.8 – 5.0 mEq/L by visit at any time through Month 6 (Long-Term Treatment Phase)

Proportions and associated exact 95% confidence interval will be presented.

5.1.3 *Subgroups*

The primary and secondary efficacy analyses may be performed for the following subgroups:

- Sex (male versus female)
- Age (12 – <18 versus 6 – <12 versus 2 – <6 years)
- Race (white versus non-white)

5.2 Safety Endpoints

Safety variables will include:

- All treatment-emergent adverse events (TEAEs)
- Reasons for dosing interruption or discontinuation
- Serious adverse events (SAEs)
- Clinical laboratory test results
- Vital signs
- ECG
- Deaths
- Laboratory safety summaries will include:

- Incidence of potassium (1) < 3.0 mEq/L, (2) < 3.5 mEq/L, (3) ≥ 5.1 mEq/L and (4) ≥ 5.5 mEq/L (measured by central laboratory)
- Incidence of serum magnesium (1) < 1.4 mg/dL (< 0.58 mmol/L), (2) < 1.2 mg/dL (< 0.49 mmol/L) and (3) < 1.0 mg/dL (< 0.41 mmol/L) (central laboratory)
- Calcium levels, phosphate levels, and serum fluoride levels will be assessed based on central laboratory analysis of samples collected at each of the scheduled study visits

5.3 Palatability Assessments

In children ≥ 6 years old, if patiromer is administered onsite, patiromer palatability assessments (taste and overall liking) will be performed on Day 1, using a 5-point facial hedonic scale. For children < 6 years old, parental or authorized legal representative assessment of the subject's acceptance of patiromer on a 5-point agreement/disagreement scale will be performed on Day 14.

5.4 Study Day and Visit Windows

The Study Day for date of first dosing is Day 1. The Study Day for all other study events is defined as follows:

- If a date is prior to the Reference Date, Study Day is defined as [date] - [Reference Date], so the Study Day for the day before date of first dose (typically the first dosing day) is defined as Day -1.
- If a date is on or after the Reference Date, Study Day is defined as [date] - [date of the first dose] +1; hence, the Study Day for the day after first dose is defined as Day 2.

The protocol specified windows for scheduled visits are included in the Schedule of Events (Appendix A and Appendix B).

Unless otherwise specified, analyses by visit will use the visit weeks reported in the database and include results collected at scheduled visits.

Analyses not limited to visits (e.g. incidence of laboratory test values within a given range, and time to event analyses) will include all available values of the variable of interest, irrespective of whether it was collected at a scheduled or unscheduled visit.

For central laboratory data, the visit information from the central laboratory will be used to determine whether a visit is scheduled or unscheduled.

For all analysis variables, unless otherwise specified, baseline is the last non-missing value of the variable on or before the first dose of any study medication.

Modifications to visit schedules may be required due to Coronavirus Disease 2019 (COVID-19). Depending on the scope of changes needed, additional analyses may be undertaken in order to clarify and assess the impact of the modifications to visit schedules. Descriptions of

the additional analyses to be done in relation to COVID-19, if any, will be provided in the SAP prior to database lock.

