3.2.4 Follow-up Period

All subjects will enter the Follow-up Period including:

- Subjects who completed the Long-Term Treatment Phase (i.e., attended the Week 26 Visit)
- Subjects who did not complete the Long-Term Treatment Phase and were withdrawn early prior to the Week 26 Visit

The Follow-up Period will consist of one visit at 7 days and one phone call at 14 days after stopping patiromer treatment. The investigator may require the Phone Call Follow-up to be converted into an onsite visit if the potassium level measured during Follow-up Visit at 7 days after stopping patiromer treatment is of concern.

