Recommendations regarding the timing of any medication as described in Section 5.5 should be followed to minimize the possibility of a drug interaction. Clinical response and/or blood levels where possible should be monitored as higher doses may be required during concomitant treatment with patiromer.

Increases in potassium levels may occur as early as 2 days after discontinuation of patiromer, which may be more likely in subjects who continue taking RAASi medications after stopping patiromer. In the Follow-Up Phase, an unscheduled visit may occur at the investigator's discretion for measurement of potassium level (See Section 6.5.1).

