7.10 Safety Analyses

7.10.1 Adverse Events

AEs and SAEs will be coded to system organ class (SOC) and preferred term (PT) with the latest available MedDRA. Adverse event analyses will include only treatment-emergent AEs (TEAEs). A TEAE is defined as any AE that newly appeared or worsened in severity following initiation of study drug administration. If the onset date of an AE is missing, the AE will be considered treatment-emergent unless there is evidence to conclude that it is not. AE listings will include all AEs.

The incidence of TEAEs will be summarized by system organ class (SOC), preferred term (PT) and severity. For those TEAEs that occur more than once during the study period, the maximum severity will be used in the summary by severity.

Descriptive statistical summaries (frequencies and percentages) will be provided for the followings:

- Overall summary of number of subjects with: any TEAE; any TEAE related to study drug; any SAE; any SAE related to study drug; any TEAE leading to study drug dose increase, dose reduction, dose interruption; any TEAE leading to study drug discontinuation
- Summary of all TEAEs by SOC, PT and severity
- Summary of TEAEs related to study drug by SOC and PT
- Summaries of TEAEs leading to study drug dose increase, dose reduction, and interruptions by SOC and PT
- Summary of TEAEs leading to early study drug discontinuation by SOC and PT
- Summary of SAEs by SOC, PT, and severity
- Summary of SAEs related to study drug by SOC and PT
- Summaries of TEAEs of special interest (e.g. allergic reactions, gastrointestinal events, renal events)

A listing for all AEs will be provided, including verbatim term, PT, SOC, severity, whether serious, relationship to study drug, onset and end date, action taken, and outcome of event will be provided. A listing of SAEs and TEAEs leading to any study drug modification or discontinuation (increase, reduction, interruption or discontinuation) will also be provided. In addition, listings will be provided for events of special interest.

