7.10.3 Clinical Laboratory Tests

For central laboratory test summaries by visit, the central laboratory measurements at scheduled visits will be used if available. The visit name from the central laboratory will be used to determine whether a visit is scheduled or unscheduled.

If a laboratory result from a visit is retested and the central laboratory subsequently determines the original result to be valid, the original result for that visit will be used in analysis, and the second (i.e. ‘retested’) value will be ignored. Otherwise, if the central laboratory detects an error through the retesting, the retested value will be used in analysis as the measurement for that visit.

The baseline central laboratory value is defined as the last non-missing central laboratory value collected on or before the date of the first dose of study medication.

All serum chemistry, hematology, serum fluoride, and plasma parathyroid hormone level results and change from baseline will be summarized with descriptive statistics at each scheduled visit.

The incidence of laboratory test results in ranges of interest will be summarized. These summaries will include but are not limited to the following:

- Serum potassium < 3.0, < 3.5, < 3.8, > 5.0, and \geq 5.5 mEq/L
- Serum magnesium < 1.4, < 1.2, and < 1.0 mg/dL
- Serum calcium > 10.2 mg/dL

Laboratory shift tables from baseline to end of dose finding period and baseline to end of treatment will be presented for serum calcium, magnesium and phosphate.

Listings will be provided for all laboratory parameters. Listings will include test results at both scheduled and unscheduled visits.

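### The any-time potassium-range counts have no start or end bound, so off-drug follow-up values are pooled with on-treatment values under the starting dose

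*SAP*

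**What the plan says.** SAP 5.4 applies one rule to "Analyses not limited to visits (e.g. incidence of laboratory test values within a given range, and time to event analyses": these "will include all available values of the variable of interest, irrespective of whether it was collected at a scheduled or unscheduled visit". SAP 7.10.3 adds that "The incidence of laboratory test results in ranges of interest will be summarized" and lists potassium thresholds at both ends of the scale, including 5.5 mEq/L and above. SAP 5.2 gives a similar list and specifies central laboratory values. None of these sections names a first or last eligible day.

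SAP 7.1 lays tables out by age cohort, starting dose and overall. The one time cut it states is for data after the start of maintenance dialysis. SAP 7.10.3 uses an end-of-treatment anchor only for shift tables of calcium, magnesium and phosphate.

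Protocol 3.2.4 sends all subjects into a Follow-up Period of "one visit at 7 days and one phone call at 14 days after stopping" patiromer. Protocol 6.3.1 draws local and central potassium at Follow-up Visit 1 (F1). Protocol 6.3.2 repeats the F1 procedures if Follow-up Visit 2 (F2) becomes an onsite visit, and protocol 6.5.1 allows unscheduled potassium draws in any phase. Protocol 5.5.1.1 explains the follow-up draws: "Increases in potassium levels may occur as early as 2 days after discontinuation of patiromer".

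For adverse events, SAP 7.10.1 states: "A TEAE is defined as any AE that newly appeared or worsened in severity following initiation of study drug administration". Protocol 9.5 likewise gives a start and no end.

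**The concern.** A child whose potassium is controlled for 26 weeks and who has 5.6 mEq/L at F1, a week after the last dose, is counted in the row for 5.5 mEq/L or above under his or her starting dose. So is a child who reaches 5.6 mEq/L at Week 10 while taking the drug. The first case says something about stopping treatment; the second says something about control at that dose. A single count cannot tell them apart.

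Safety and tolerability are the secondary objective, and the study is meant to support a recommended starting dose in each age group. With 12 children at that dose, one child moves a rate by 1/12 = 8.3 percentage points. Follow-up sampling is also not neutral: extra draws may be made at the investigator's discretion because a rise after stopping is possible.

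**Working it through.** **The plan's own figure.** Neither document gives a rate of hyperkalemia on treatment or after stopping, so there is no figure of theirs to reproduce on this point. The precision statement in SAP 2.3 does reproduce: for 12 successes in 12, the two-sided exact lower limit is 0.025^(1/12) = 0.735, stated as 73%. Only the cohort size of 12 is used below.

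**Step 1: which samples the rule admits.**
- On treatment, a child with every visit has Day 3, Day 7, Day 14 and 8 long-term visits: 3 + 8 = 11 scheduled post-baseline central samples. Four of these visits (Day 3, Weeks 3, 10 and 22) can be omitted, leaving 7.
- The last dose is taken the day before Week 26 (protocol 5.3.3 and 6.2.6), so the Week 26 sample falls 1 day after the last dose.
- F1 is at 7 ± 3 days after stopping, that is days 4 to 10. The whole window lies beyond the 2 days in protocol 5.5.1.1. F1 adds one scheduled off-drug sample; unscheduled visits and an onsite F2 can add more.
- Before dosing, entry requires local potassium of 5.1 to < 6.5 mEq/L (protocol 4.1), and a central sample is drawn at the converted screening/Day 1 visit. With no start bound, the count above 5.0 mEq/L would approach 100% whatever happened later. The follow-up problem is therefore clearest at 5.5 mEq/L and above, or once counts are limited to post-dose values.

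**Step 2: effect on a count.** Let a be the share of children at or above the threshold on treatment and b the share at or above it after stopping. Pre-dose values are left out here. The pooled share depends on how far the two groups overlap:
- full overlap: max(a, b)
- independence: 1 − (1 − a)(1 − b)

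With a = 20% and b = 40%, both assumed:
- full overlap: max(0.20, 0.40) = 40%, or 4.8 of 12 children
- independence: 1 − 0.80 × 0.60 = 52%, or 6.2 of 12 children
- on-treatment share alone: 20%, or 2.4 of 12 children

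With a = b = 20% and full overlap, the pooled share is 20% and nothing is added.

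**Step 3: the same without assuming independence.** Let r be the share of children below the threshold on treatment who reach it only after stopping. The pooled share is a + (1 − a) × r, and the off-drug-only part of that count is (1 − a) × r divided by the pooled share. All inputs are assumed.

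| a | r | Pooled share | Off-drug-only part of the count |
|---|---|---|---|
| 10% | 10% | 19% | 47% |
| 10% | 50% | 55% | 82% |
| 30% | 10% | 37% | 19% |
| 30% | 30% | 51% | 41% |
| 50% | 10% | 55% | 9% |
| 50% | 50% | 75% | 33% |

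When r = 0 the pooled and on-treatment shares agree. The table shows how sensitive the count could be; it does not predict the result.

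**The case against.** The strongest reply is that other outputs already separate the periods. SAP 7.10.3 summarizes serum chemistry, which includes potassium, at each scheduled visit, and F1 is a scheduled visit. SAP 7.9.2 plots central potassium and its mean change by visit. The secondary endpoint, the proportion in 3.8 to 5.0 mEq/L by visit, runs only through Month 6. Laboratory listings include unscheduled visits, and adverse event listings carry onset dates. All of this stands. A reader might infer that the tables hide what happens after stopping, and the documents do not support that. What remains is that by-visit summaries do not show how many children in an any-time count crossed the threshold only off drug.

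A reader might also infer that the protocol expects a rebound and that the tables report it as hyperkalemia on patiromer. The protocol says only that rises may occur, and that they may be more likely with continued RAAS inhibitors. No table carries an on-patiromer label. The pooling arises because there is no off-drug category.

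A third tempting reading is that the open-ended TEAE definition is an error. It is not. Protocol and SAP agree on it, subjects are deliberately followed for 2 weeks after the last dose (protocol 4.3), and counting those events is a defensible, inclusive choice. Nor is a value of 5.6 mEq/L automatically an adverse event: protocol 8.1 requires symptoms or a diagnosis, discontinuation, treatment or referral, or judged clinical significance.

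Finally, the sentence in SAP 5.4 is mainly about scheduled versus unscheduled collection. That is fair, but no other section supplies the missing bounds.

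**Conclusion.** The point holds for the any-time potassium-range counts. As written, they mix values from before dosing, during treatment and after stopping under one starting dose, and the count at 5.5 mEq/L or above cannot be read as control on treatment. The primary and secondary efficacy endpoints are unaffected, and by-visit outputs show F1 separately.

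The size cannot be derived from the documents. On the assumed 20% and 40%, the pooled count is 40% to 52% as dependence runs from full overlap to independence, against 20% on treatment. A reader might take such figures as a measured distortion. They are not: both rates and the degree of overlap are assumptions, and the same children may well exceed the threshold in both periods. This is a clarification worth making before database lock in a descriptive, single-arm study.

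**What to change.** In SAP 5.4 and 7.10.3, count potassium-range incidence in two columns shown side by side:

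- **On treatment:** central values from after the first dose through the day after the last dose. This includes the Week 26 visit.
- **After treatment:** later values through the end of follow-up, including any Early Termination sample drawn more than one day after the last dose. Protocol 6.4 lets that visit take place as soon as possible after the last dose, so the case needs stating.

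Use as denominator the dosed children with at least one central potassium value in that window. State that analysis time at a prescribed 0 g/day within the treatment phase, which protocol 4.4 and 5.2.1 allow, stays in the on-treatment column and is flagged. Keep the existing exclusion of data after the start of dialysis.

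In SAP 7.10.1, keep the TEAE definition and the pooled total, and add a row splitting hyperkalemia TEAEs by onset on treatment or after treatment.

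The cost is SAP wording and one extra column set, built from visit and last-dose dates already collected. The downside is smaller counts in each column. No dose, visit or clinical rule changes.
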